6.7 Snowball Recruitment: If a participant requests a screening/enrolment link to share with their network at any time, we will share a customized link to the Chalo!2.0 study information page. They can request this link either by texting/WhatsApp on the study phone number or by contacting our VPeers on a recruitment platform. If a participant does not request a link by the 3-month mark of enrolment in the study, we will proactively ask participants whether they are willing to share a customized link among their network, via WhatsApp or SMS. All links lead to the Chalo! 2.0 study information page. Rationale: Participants may already be sharing screening/enrolment links among their network. This strategy allows us to monitor when participants refer other individuals to the study. We will not provide any monetary benefits/ support for sharing the link.

7. Randomization and blinding. Subjects meeting all eligibility criteria will be randomized to one of three study arms. Participants will be assigned either to **CHALO! 2.0** (intervention), to an Attention-Matched Control, or to a Digital Coupon for free HIV testing only arm. After baseline survey completion, The research team at HST will use random blocked design, with a fixed block size, to stratify randomization by prior HIV testing history (never tested vs. not tested in >6 months). To further minimize bias in group allocation and analysis, a data manager who has no contact with study participants will (1) assign them to study group (intervention or controls), (2) notify our technology consultant of group assignment by providing the consultant each week with a list of mobile numbers and which set of contents each number should be programmed to receive, and (3) store allocation sequences in a password-protected encrypted file. Participants will be unaware of arm assignment and will receive automated messages to complete online surveys. Study staff collecting HIV testing and linkage-to-care outcomes will also be blinded to study arm. Finally, HST’s online peer counselors and navigators will not be informed of study hypothesis.

8. Data Collection.

Table 2: Data sources and measures						
Measure	Study Instrument	Assessment Month				
Outcomes: HIV testing and linkage to care		0	3	6	12	18
HIV testing	Lab report (via digital coupon); self-report	●	●	●	●	●
Linkage to prevention/treatment (PrEP, counseling, ART)	HST’s healthcare worker log; HST clinic record; self-report	●	●	●	●	●
Covariates						

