When participants present the coupons at any testing site, the tester-counselor (at HST sites) or lab technician (at the private lab sites) will enter the coupon code using an online coupon form. This system will register the coupon as being used, with time, date, and location of usage. Once test results are available, they will be entered in a manner specific to the testing site. At HST, the tester-counselor will enter test results directly into an Avegen HM form. If the coupon is used at the private lab, the data manager will retrieve results from the lab's secure online portal (along with the coupon use data) and enter it into the Avegen HM database. Two strategies will be used to capture testing data if a participant does not use the digital coupon provided by the trial. As described above, counselor-based testing that occurs at HST will be identified when the data manager cross-checks mobile phone numbers and emails for clients obtaining HIV tests against participant contact information. (At HST, contact information is provided by >99% of clients,⁹⁰ as required by Indian guidelines.⁹¹) Second, testing that occurs outside both HST and our private lab partner is expected to be rare, as subjects will receive free tests through the private lab (41 sites across Mumbai) or through HIV self-testing only if they use the digital coupon provided. Further, HST's 3 sites are the only MSM-specific free testing sites in Mumbai. In the very rare event that a participant does report testing elsewhere, this will be captured in the online survey, which will ask for the name and location and for the participant to upload a picture through secure link of their test completion result.

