A1d. Special vulnerable populations. We will not include fetuses, neonates, children, pregnant women, prisoners, or institutionalized individuals in the proposed research. Men who have sex with men are vulnerable due to their status as a stigmatized population in society and further stigmatization could be possible if their status as a participant in an HIV prevention intervention is revealed. In the following sections, we discuss these risks and procedures to minimize them and believe that the risks to participation in the proposed study are minimal.

A1e. Study group assignment procedures, and rationale for intervention's dose, frequency and administration. Subjects meeting all eligibility criteria will be randomized to one of three study arms. Participants will be assigned either to CHALO! 2.0 (intervention), to an Attention-Matched Control, or to a Digital Coupon for free HIV testing only arm. Randomization will occur in a random blocked design, stratified by HIV testing history (never tested/unaware of results vs. previously tested). To minimize bias in treatment group allocation, the data manager will store the allocation sequence using a password-protected file, and has no contact with study participants. Participants will receive automated messages with online

survey links to complete study assessments, and study staff extracting medical record/log data to ascertain linkage-to-care outcomes, will be blinded to treatment group allocation and will have no contact with study participants.

During the 12-weeks intervention period, participants assigned to either CHALO! 2.0 (intervention) or the Attention-Matched Control (AM) arm will be exposed to twice-weekly digital messaging, including text, brief videos, inform graphics, etc. via an online messaging site. However, the digital message for participants in the CHALO! 2.0 arm will include information regarding HIV testing, accessing treatment and prevention care with a focus on targeting information, motivation, and behavioral skills, while the information in the AM arm will focus on general health topics (e.g., diabetes, obesity, nutrition, exercise). Participants in the digital coupon only arm will not receive any messages aside from the reminders to complete study assessments. We are providing twice weekly contents as this was determined in the past to be acceptable, not intrusive and higher frequency may actually be detrimental.

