This system will also alert study staff that a coupon was used with information about which coupon, so that study staff can follow-up with clients if needed about their results. If the coupon is used at HST, the tester/counselor will enter test results directly into a front-end HIV testing result form on Avegen HM (coupon-code and associated test result); if the coupon is used at a private lab, study staff will retrieve results from the lab's online portal, and then enter the test results into a front-end HIV testing result form on Avegen HM.

This approach has been generally used previously, including in a recent feasibility pilot by our private laboratory partner, and will enable real-time monitoring of test results, and accurate follow-up for clients.

Lab HIV testing data: Additionally, HST currently collects and verifies mobile phone numbers for clients coming in for testing to enable follow-up and linkage-to-care and as a requirement per Indian guidelines and requirements for testing. Subjects will only be able to receive the free test at the private lab or HIV self-test if they show the coupon. These steps will help ensure thorough assessment of our primary outcome and facilitate appropriate follow-up.

Linkage-to-care outcomes for HIV negative and positive individuals will be abstracted from HST's healthcare worker log, which contains information about linkage status and outcomes (HIV treatment registration, ART initiation, follow-up) or from HST's counseling and clinic utilization records which are housed on a computerized information system (CIS) at HST. Data from the HST healthcare worker log and the CIS can be linked to an individual's mobile phone number which will be how we match a participant's use of HST services. The data manager at HST on a monthly basis, will scan and match participant phone numbers to those in CIS; for any matches, that data will be extracted and merged into the Avegen HM database. The healthcare worker log also contains information about linkage/referrals to private HIV treatment clinics and for primary care/PrEP. Currently, HST refers clients interested in PrEP to two providers in Mumbai (vetted by HST to

provide MSM competent services). HST will also begin offering PrEP this summer to its patients, and will thus be available moving forward for all HST clients, including study participants.

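### As written, the data manager who holds the allocation also retrieves and matches outcome records, so the stated blinding of outcome collection does not hold for those pathways

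*Combined protocol and SAP*

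**What the plan says.** **Allocation.** Section 7 (Randomization and blinding) says that "a data manager who has no contact with study participants will (1) assign them to study group". The same person notifies the technology consultant by "providing the consultant each week with a list of mobile numbers and which set of contents each number should be programmed to receive", and stores the sequence. A1e repeats that "the data manager will store the allocation sequence using a password-protected file, and has no contact with study participants".

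**Blinding.** Section 7 adds: "Study staff collecting HIV testing and linkage-to-care outcomes will also be blinded to study arm". A1e says of the staff who extract record and log data on linkage that they "will be blinded to treatment group allocation and will have no contact with study participants". Neither place makes an exception for the data manager.

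**Outcome collection.** Section 8.2 says that counselor-based tests at HST done without the coupon are found "when the data manager cross-checks mobile phone numbers and emails for clients obtaining HIV tests against participant contact information". It also has the data manager fetch private-laboratory results from the laboratory's portal and enter them. For that last task A2 names only study staff. A2 has the data manager download and merge coupon-use data twice weekly. On linkage, A2 says: "The data manager at HST on a monthly basis, will scan and match participant phone numbers to those in CIS". Section 8.3 gives the same task to the HST data manager, but weekly.

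**The concern.** Having no contact with participants stops the data manager from influencing what participants do. It does not blind the data manager when outcomes are looked up. On the plain reading, someone who has each participant's arm in routine weekly use also searches for and merges records that feed both primary outcomes: a verified HIV test within 6 months (Aim 1) and linkage to prevention (Aim 2).

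What is at stake is differential effort. An unmatched number might be pursued harder in one arm, or a portal record noticed later in another. Participants in the two messaging arms see the content they receive, so blinded ascertainment is one of the main protections the plan claims. If the roles stay as described, the trial report could not claim it for these pathways.

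**Working it through.** No figure in the plan bears on this point. The check is therefore a trace of who does what, followed by an illustration of size.

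**Trace of roles**

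| Step | Who, and where stated | Bears on |
|---|---|---|
| Assign arms, store sequence | Data manager (7, A1e) | Knowledge of arm |
| Weekly list of number by content | Data manager (7) | Knowledge of arm |
| Result of couponed test at HST | Tester-counselor (8.2) | Aim 1 |
| Registration of coupon use | Testing-site staff enter the code; the system records time, date and place (8.2, A2) | Aim 1 |
| Download and merge of coupon use | Data manager (A2) | Aim 1 |
| Private-laboratory result | Data manager (8.2); study staff (A2) | Aim 1 |
| Uncouponed counselor test at HST | Data manager (8.2) | Aim 1 |
| Linkage records in HST's system | Data manager, weekly (8.3) or monthly (A2) | Aim 2 |
| Message receipt and viewing | Data manager (A2) | Partial knowledge of arm |

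Three things follow.

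1. The allocation list is keyed by mobile number. The search for uncouponed tests and for linkage records also runs on mobile number (with email for the former). The allocation list and the outcome search share a key.
2. No section names a second data manager, a masked matching file, a written matching rule or an independent check.
3. Arm is visible by other routes too. Message-view data exist only for the two messaging arms (A2), and the personalized links lead to arm-specific webpages (2.1, 2.2).

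**Illustration of size**

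From Section 13.2: n = 300 per arm, two-sided alpha 0.025, and a 35% testing rate (the attention-matched control figure). The pooled normal approximation used here comes close to Table 3: 93.2% for 0.50 vs 0.35 (stated >93%), 58.8% for 0.50 vs 0.40 (stated >59%) and 15.5% for 0.50 vs 0.45 (stated >15%).

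The remaining inputs are assumptions and are not in the documents. There is no true effect. A share u of tests reaches the database only through the data manager. A fraction m of those is missed, in the control arm only.

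- Spurious difference: d = 0.35 × u × m, so the recorded control rate is 0.35 − d.
- Null SE: se0 = √(2·p̄(1−p̄)/300), where p̄ is the mean of the two recorded rates. The unpooled SE is se1.
- Rejection rate: 1 − Φ((2.2414·se0 − d)/se1) + Φ((−2.2414·se0 − d)/se1).

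Worked case, u = 50% and m = 20%: d = 0.35 × 0.5 × 0.2 = 0.035; recorded rates 0.35 and 0.315; p̄ = 0.3325; se0 = 0.03847; se1 = 0.03844. The upper tail is 1 − Φ(1.332) = 0.091, the lower about 0.001, in total 9.2%.

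| u | m | d (points) | Rejection rate (nominal 2.5%) |
|---|---|---|---|
| 10% | 10% | 0.35 | 2.6% |
| 20% | 20% | 1.4 | 3.5% |
| 30% | 20% | 2.1 | 4.7% |
| 50% | 20% | 3.5 | 9.2% |

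If the same fraction were missed in every arm, then under no true effect d would be zero and the error rate would not rise.

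**The case against.** The strongest reply is that little discretion is involved.

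- Couponed HST results are entered by the tester-counselor. Private-laboratory tests and self-tests require the coupon (2.4), its use is registered by the system, and study staff are alerted (A2). The laboratory keeps its own result in its portal. The data manager copies these records and does not create them, so an omission would leave a trace.
- Only uncouponed counselor tests at HST depend on the data manager to be found. Numbers are verified on both sides, and over 99% of HST clients give contact details (8.2).
- Linkage is recorded upstream by clinic and healthcare-worker staff. The data manager is said to cross-check, match, extract and merge, not to classify. Any counseling counts toward the composite (Section 10).
- A1e speaks of separate, blinded extraction staff, which suggests that the authors may have had a different role in mind.

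Most of this stands, and it limits the likely harm. A reader might infer that one unblinded person ascertains both primary outcomes for everyone, decides which tests count and classifies linkage by judgement. The documents do not support that. Nor does the Background figure, that over half of individuals in earlier online studies were tested at a private laboratory or clinic, measure how many tests here would depend on the data manager. The 50% row in the illustration treats such tests as discoverable only by that person, although each is coupon-logged.

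The reply does not rescue the blinding statement. A mechanical match made by someone who knows the arm is still unblinded, and no matching rule or check is written down.

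**Conclusion.** The concern holds in a limited form. As written, the claim of blinded outcome collection in Section 7 and A1e is contradicted for four pathways: uncouponed HST tests, linkage records in HST's system, the merging of coupon-use data and, under Section 8.2 but not A2, private-laboratory results. It is not contradicted for results of couponed tests entered at HST.

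The conclusion rests on reading the data manager of Sections 7, 8.2, 8.3, A1e and A2 as one person. A single title is used and no other is named, so this is the natural reading, but it is not stated outright.

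No bias is shown, and its size cannot be derived from the documents. In the assumed scenarios the spurious difference runs from 0.35 to 3.5 points, against planned differences of 35 points (70% − 35%) and 40 points (70% − 30%). It could not produce an effect of the planned size. It would matter more if the true effect were small. The point is worth correcting because both primary outcomes are touched and the correction is cheap.

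**What to change.** 1. Let a different existing role hold and apply the allocation: the survey platform, or a coordinating-site analyst working by study ID and randomization stratum. The second option fits the rule under Research Sites that coordinating-site staff see no identifiers.
2. Send the arm list by study ID directly to the technology consultant. Messages are programmed by mobile number, so the data manager must separately give the consultant an ID-to-phone key that carries no arm.
3. Retrieve and match outcomes by a fixed exact-match rule, on a file without arm codes, message-view data or arm-specific webpage links, until outcomes are locked.
4. Reconcile Section 8.2 with A2 on who retrieves private-laboratory results, and Section 8.3 with A2 on weekly or monthly matching of linkage records.
5. If the roles are not separated, remove the blinding statement in Section 7 and A1e or limit it to the pathways where it is true.

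The cost is a small amount of extra file handling and a short amendment.
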